## 1. SYNOPSIS

Name of Sponsor/Company: Galera Therapeutics, Inc.	
Name of Investigational Product: GC4419 (avasopasem manganese)	
Name of Active Ingredient: GC4419 (avasopasem manganese)	
Title of Study:  An Open Label Multi-Center Study of the Effects of Superoxide Dismutase Mimetic GC4419 when Administered to Reduce the Incidence and Severity of Severe Oral Mucositis (SOM) Associated with Chemoradiotherapy for Locally Advanced, Non-Metastatic Head and Neck Cancer	
Number of Study Center(s):  Approximately 30 centers in selected countries in Europe	
Estimated Enrollment Period:  Approximately 12 months	
Studied period (years):  First subject enrolled: June 2020 Estimated date last subject enrolled: 4 th quarter 2020 Estimated date for primary results: 2 nd quarter 2021	Phase of development: 2
Objectives:  Primary Objective: 

To assess the safety and tolerability of GC4419 administered intravenously (IV) to subjects receiving post-operative or definitive therapy with single-agent cisplatin plus Intensity-Modulated Radiation Therapy (IMRT) for locally advanced, non-metastatic squamous cell carcinoma (SCC) of the head and neck

 Secondary Objective: 

To assess the incidence of severe oral mucositis (SOM; World Health Organization Grade 3 or 4) in the study population

	
Endpoints:  Primary Endpoint: 

Frequency, duration, and severity of AEs and serious AEs (SAEs);

Incidence and shifts of clinically significant laboratory abnormalities

	

**Secondary Endpoints:**

- Cumulative incidence of SOM, defined as any occurrence of WHO Grade 3-4 OM, from the first IMRT fraction through the end of the study treatment period (last day of IMRT)
- Cumulative incidence of WHO Grade 4 OM and days of Grade 4 OM from the first IMRT fraction through the end of the study treatment period (last day of IMRT)
- Cumulative incidence of SOM, and days of SOM, from the first IMRT fraction through two weeks after the end of IMRT

**Methodology:**

GTI-4419-202 is an open-label, multi-center international study conducted to evaluate the effects of GC4419 when administered IV in combination with IMRT/cisplatin to subjects with head and neck cancer, who are at high risk for SOM.

Subjects will receive 90 mg GC4419 per day (60 min IV infusion to complete within 4 hours prior to IMRT), concurrent with daily fractions of IMRT (2.0-2.2 Gy) to a total of 60-72 Gy over approximately 7 weeks, plus cisplatin administered 100 mg/m^2 once every three weeks for 3 doses or 40 mg/m^2 once weekly for 6-7 doses (Investigator's choice)

*Note: Planned radiation fields must include at least 2 oral sites (left and right buccal mucosa, floor of mouth, left and right lateral tongue, soft palate) with each site receiving a cumulative dose of at least 50 Gy.*

If IMRT is not administered on any given day due to a treatment break or unforeseen circumstances, GC4419 should not be administered on that day.

All subjects will be assessed twice weekly for OM per WHO grading criteria until 28 days post end of study treatment period (last day of IMRT).

**Number of subjects (planned):**

Up to 70 total subjects

**Diagnosis and main criteria for inclusion:**

**Inclusion Criteria:**

1. Pathologically-confirmed diagnosis of locally advanced squamous cell carcinoma of the head and neck that will be treated with cisplatin plus concurrent IMRT.  
*Note: Patients with unknown primary tumors whose treatment plan matches the requirements specified in Inclusion Criteria #2 and #3 below are eligible for the study.*
2. Treatment plan to receive a continuous course of IMRT delivered as single daily fractions of 2.0 to 2.2 Gy with a cumulative radiation dose of 60-72 Gy. Planned radiation fields must include at least 2 oral sites (left and right buccal mucosa, floor of mouth, left and right lateral tongue, soft palate) with each site receiving a cumulative dose of at least 50 Gy.  
*Note: Unavoidable doses of at least 50 Gy, to include entrance, exit, and scatter doses, still constitute planned radiation.*
3. Patients who have had prior surgery are eligible, provided they have fully recovered from surgery, and patients who may have surgery in the future are eligible.
4. Treatment plan to receive standard cisplatin monotherapy administered either every three weeks (100 mg/m^2 for 3 doses) or weekly (40 mg/m^2 for 6-7 doses). The decision on which cisplatin regimen to use in combination with IMRT and GC4419 will be at the discretion of the Investigator.
5. Age 18 years or older
6. Eastern Cooperative Oncology Group (ECOG) performance status ≤ 2

7. Adequate hematologic function as indicated by:
  - Absolute neutrophil counts (ANC)  $\geq 1,500/\text{mm}^3$
  - Hemoglobin (Hgb)  $\geq 9.0 \text{ g/dL}$
  - Platelet count  $\geq 100,000/\text{mm}^3$
8. Adequate renal and liver function as indicated by:
  - Serum creatinine acceptable for treatment with cisplatin per institutional guidelines
  - Total bilirubin  $\leq 1.5 \times$  upper-normal limit (ULN)
  - Aspartate aminotransferase (AST) and alanine aminotransferase (ALT)  $\leq 2.5 \times$  ULN
  - Alkaline phosphatase  $\leq 2.5 \times$  ULN
9. Serum pregnancy test negative for women of childbearing potential
10. Males and females must agree to use highly effective method of contraception starting prior to the first day of treatment and continuing after the last dose of GC4419 for 30 days (females) or 90 days (males)
11. Properly obtained written informed consent

**Exclusion Criteria:**

1. Metastatic disease
2. Prior radiotherapy to the region of the study cancer or adjacent anatomical sites or more than 25% of total body marrow-bearing area (potentially interfering with chemo-tolerance)
3. Prior induction chemotherapy or plans for chemotherapy to be administered only sequentially, not concurrently, with IMRT
4. Planned concurrent chemotherapy other than single agent cisplatin
5. Receiving any approved or investigational anti-cancer agent other than those provided for in this study
6. Concurrent participation in another interventional clinical study or use of another investigational agent within 30 days of first dose of GC4419

*Note: Patients who are participating in non-interventional clinical studies (e.g., QOL, imaging, observational, follow-up studies, etc.) are eligible, regardless of the timing of participation.*

7. Inability to eat soft solid food at baseline for reasons other than mouth soreness after surgery or dental procedures
8. Complete reliance on parenteral or gastrointestinal tube-delivered nutrition at baseline  
*Note: Patients who have gastrostomy tubes prophylactically placed are eligible. Patients receiving supplemental nutrition through a gastrostomy tube at baseline may be eligible depending on diet.*
9. Malignant tumors other than head and neck cancer (HNC) within the last 5 years, unless treated definitively and with low risk of recurrence in the judgment of the treating Investigator
10. Active infectious disease excluding oral candidiasis
11. Presence of oral mucositis at baseline. Subjects with mouth or throat pain solely due to post-operative effects are eligible, however.
12. Known history of human immunodeficiency virus (HIV) or active hepatitis B/C (patients who have been vaccinated for hepatitis B and do not have a history of infection are eligible)
13. Female patients who are pregnant or breastfeeding
14. Known allergies or intolerance to cisplatin and similar platinum-containing compounds

15. Requirement for concurrent treatment with nitrates or other drugs that may, in the judgment of the treating Investigator, create a risk for a precipitous decrease in blood pressure.
 
16. Medical history that includes any condition, or requires the use of concomitant medications which, in the Investigator's judgment, are associated with or create a risk of increased carotid sinus sensitivity, symptomatic bradycardia, or syncopal episodes.

--

**Investigational product, dosage and mode of administration:**

GC4419 is formulated as a clear solution at a concentration of 9 mg/mL in 26 mM sodium bicarbonate-buffered 0.9 wt. % saline for parenteral administration (drug product). GC4419 will be presented in single use vials, one vial per day. Vials will be filled with 11 mL of GC4419, of which 10 mL be added into a 250 mL bag of normal saline, for daily IV administration over 60 minutes. GC4419 will be administered concurrent with daily fractions of IMRT (2.0-2.2 Gy) to a total of 60-72 Gy over 7 weeks, plus cisplatin administered 100 mg/m^2 once every three weeks for 3 doses or 40 mg/m^2 once weekly for 6-7 doses (Investigator's choice).

**Duration of treatment:**

Approximately 35 doses, on days in which IMRT is administered, Monday-Friday (M-F), for approximately 7 weeks. GC4419 will be administered within 4 hours prior to each IMRT treatment.

**Reference therapy, dosage and mode of administration:**

Not applicable

**Criteria for evaluation:**

**Safety:**

National Cancer Institute (NCI) - Common Terminology Criteria for Adverse Events (CTCAE), version 5.0

Clinical Laboratory Assessment: A central laboratory vendor will be utilized.

**Efficacy:**

WHO Criteria for OM

**Toxicity Management:**

Toxicity requiring 25% GC4419 dose reduction:

- Grade 2 or greater hypotension within 2 hours after the start of GC4419 infusion
- Grade 3-4 adverse events (AEs) judged by the Investigator to be likely attributable to the study infusion.

Dose reductions of GC4419 should be done in increments of 25% of the starting dose. Two dose reductions for toxicity will be permitted per subject. Subjects unable to tolerate GC4419 after 2 dose reductions must discontinue treatment with GC4419 but should continue with cisplatin/IMRT and other study assessments and procedures, with the concurrence of the treating Investigator, if the subject maintains informed consent to do so.

For other toxicities (including those attributable to cisplatin and IMRT): management per institutional and American Society of Clinical Oncology (ASCO) guidelines and Investigator judgment. Cisplatin toxicities should be managed by modification of the cisplatin dose and schedule, not by substitution of another systemic agent.

Multinational Association of Supportive Care in Cancer (MASCC)/International Society of Oral Cavity (ISOO) Oral Care Education Materials and patient instructions for oral hygiene will be strongly recommended, and a summary appended to the protocol ([Appendix 6](#)).

OM will NOT be considered an AE requiring dose modification for the purposes of this study.

### **Concomitant Medications/Treatments:**

Investigators may prescribe concomitant medication or supportive therapy deemed necessary to provide adequate supportive care for complications other than OM, e.g., antiemetics, systemic antibiotics, hydration to prevent renal damage, etc.

Hematopoietic growth factor use is permitted per ASCO guidelines. Following ASCO (and MASCC) guidelines for the prevention and management of chemotherapy-induced nausea and vomiting (CINV) is strongly encouraged.

Oral care per MASCC/ISOO Oral Care Education Materials (summarized in [Appendix 6](#)) is strongly recommended for all subjects as part of standard of care.

Oral topical lidocaine is permitted.

Diphenhydramine (Benadryl®) administered as tablets or by injection is permitted.

The following must not be used:

- Nitrates, phosphodiesterase type 5 (PDE 5) inhibitors (e.g., sildenafil, tadalafil, or similar agents) or other drugs that in the judgment of the treating Investigator could create a risk of a precipitous decrease in blood pressure are prohibited until at least 24 hours after the last dose of GC4419
- Pyridostigmine or other drugs that in the judgment of the treating Investigator could create a risk of increased carotid sinus sensitivity, symptomatic bradycardia, or syncopal episodes.
- Palifermin (Kepivance®) or another keratinocyte or fibroblast growth factor
- Amifostine (Ethyol®)
- Benzydamine (Difflam®, Pharixia®, Tantum Verde)
- Low-level laser treatment
- Glutamine applied topically
- GM-CSF applied topically
- ‘Mouthwashes’ that include the following:
  - Chlorhexidine
  - Hydrogen peroxide
  - Diphenhydramine (Benadryl®) liquid formulation
  - Tetracycline
  - Any other listed disallowed medications
- MuGard™, Gelclair®, Episil®, or other barrier devices
- Caphosol®
- Povidone-iodine rinses
- Steroid rinses
- Sucralfate in suspension form (use of sucralfate tablets is not proscribed)
- Biologic response modifiers – except systemic hematopoietic growth factors for the management of anemia or myelosuppression
- Concurrent approved or investigational anti-cancer therapy (e.g., chemotherapy, immunotherapy, targeted therapy, hormone and biologic therapy) other than the Protocol regimen
- Other investigational agents

All medication restrictions end after IMRT is completed unless otherwise noted.

**Statistical methods:**

The primary objective of this study is to further assess the safety profile of GC4419, with efficacy objectives of cumulative incidence of SOM, days of SOM, and tumor outcome key secondary efficacy endpoints. No formal statistical hypothesis testing is prespecified for the primary safety objectives. A sample size of up to 70 subjects has been selected to obtain adequate safety and efficacy subject data to compare with observed data in North American studies and historical controls for IMRT with Cisplatin. These results will also contribute to pooled analysis of an overall minimum safety database of 300 subjects with head and neck cancer who will, across all studies of GC4419, have received a full course of GC4419 at the intended dose (90 mg), schedule (1-hour infusion, 5 days/week, prior to IMRT), and duration (single course of 6-7 weeks) in combination with concurrent IMRT and cisplatin. The overall safety database size of 300 will allow for detection with 95% probability of adverse events of 1% true incidence in at least 1 subject.

As this is the first study of this drug in EU, the efficacy analysis will allow for comparison to North American results and historical controls and confirm uniformity in applying OM scoring procedures used for WHO criteria that could be used to inform future development programs.

Safety and efficacy will be assessed on an "intent to treat" (ITT) population consisting of all enrolled subjects who receive at least one dose of GC4419, and on a "per protocol" population consisting of subjects who receive at least 60 Gy of IMRT and at least 5 weeks (25 doses) of GC4419. Overall rates of adverse events, serious adverse events, and SOM/Grade 4 OM incidence will be summarized descriptively.

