GC4419 was studied in a Phase 1b/2a clinical study, GT-001 (NCT01921426, [Anderson, Sonis, et al. 2018](#)) and Phase 2b study, GT-201 (NCT02508389). In study GT-001, GC4419 was administered throughout the full 6- to 7-week course of chemo-radiotherapy (CRT) at doses of either 30 or 90 mg, Monday-Friday (M-F), and appeared to substantially reduce the duration, incidence, and overall severity (defined here as the incidence specifically of Grade 4) of severe OM compared with historical expectations (data are based on 43 evaluable subjects). Further, GC4419 did not appear to increase the known toxicity of the CRT regimen (IMRT plus concurrent cisplatin), nor did it appear to interfere with tumor response to CRT assessed through 1 year post therapy (for details see [Anderson, Sonis, et al. 2018](#) and the Investigator's Brochure). These results supported the design of the randomized, double-blind, placebo-controlled, Phase 2b study GT-201, with two GC4419 doses of 30 and 90 mg selected for comparison with placebo and administered 5 days/week. As in GT-001, patients eligible for GT-201 were required to have locally advanced squamous cell carcinoma of the oral cavity (OC) or oropharynx (OP), with their standard care calling for concurrent IMRT and cisplatin. Results from 223 randomized subjects indicated that GC4419 at daily dose of 90 mg resulted in statistically significant reduction on the primary endpoint, severe OM duration, for subjects on the 90 mg arm compared to placebo, as determined by the non-parametric Van Elteren test. The median duration of SOM, as defined in the protocol, was 1.5 days for subjects receiving 90 mg of GC4419 vs 19 days for subjects receiving placebo ( $p=0.024$ ). Also, the incidence of SOM during the IMRT treatment period was 43% for subjects receiving 90 mg of GC4419 vs 65% for subjects receiving placebo (nominal  $p$  value=0.009), a relative reduction of approximately 34%. The safety profile of GC4419 in combination with the IMRT/platinum regimen in GT-201 study was acceptable; safety results with both the 90 mg dose and the 30 mg dose were similar to those with placebo (Anderson et al, 2019). Two year follow up for standard tumor outcomes (progression-free survival, overall survival, local control, distant metastasis-free rate) did not vary among the three study arms (Anderson et al, 2020).

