Based on these results, a randomized, double-blind, placebo-controlled Phase 3 trial, GTI-4419-301, has been initiated in the US and Canada. This study is of substantially the same design as GT-201, and is limited to patients with tumors of the oral cavity and oropharynx, as was the case in GT-001 and GT-201. GTI-4419-301 is a 2-arm study, with eligible subjects randomized in a 3:2 ratio to 90 mg of GC4419 or placebo in combination with IMRT/cisplatin. In accordance with discussions with regulatory authorities, the primary endpoint of GTI-4419-301 is the incidence of SOM during the study treatment period (through the last fraction of IMRT). Secondary efficacy endpoints are incidence of Grade 4 OM through the study treatment period, and the number of days of SOM or Grade 4 OM, defined as was "duration" of SOM in GT-201. The sample size is 335 randomized subjects who receive at least one dose of GC4419 or placebo.

However, additional data will be needed to permit assessment of the safety of GC4419 at the intended dose, schedule, and duration of administration, in combination with IMRT/cisplatin, to

identify adverse events with an overall frequency of approximately 1%. The present study will obtain these data along with further exploratory information about the incidence of SOM in patients receiving 4419 plus IMRT/cisplatin for a range of head and neck cancers.

Additional details about the pathogenesis of OM, the mechanism of action of GC4419, and the results of non-clinical testing as well as the clinical trials GT-001 and GT-201 are provided in the Investigator's Brochure.

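### The synopsis names tumor outcome a key secondary efficacy endpoint that the rest of the protocol does not deliver, and its planned North American comparison is confounded with tumor site

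*Combined protocol and SAP*

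**What the plan says.** **Tumor outcome.** The statistical methods paragraph of the synopsis sets out "efficacy objectives of cumulative incidence of SOM, days of SOM, and tumor outcome key secondary efficacy endpoints". The synopsis list of secondary endpoints has three items, all on oral mucositis (OM); the last is "Cumulative incidence of SOM, and days of SOM, from the first IMRT fraction through two weeks after the end of IMRT". Section 5.2 repeats those three items, and Section 5.1 has SOM incidence as the only secondary objective.

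**Comparison.** The same paragraph says the sample size was chosen to "obtain adequate safety and efficacy subject data to compare with observed data in North American studies and historical controls". It adds that "the efficacy analysis will allow for comparison to North American results and historical controls" and that this analysis will also "confirm uniformity in applying OM scoring procedures used for WHO criteria".

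**Populations.** Section 4.2 says that "a randomized, double-blind, placebo-controlled Phase 3 trial, GTI-4419-301, has been initiated in the US and Canada" and that this trial "is limited to patients with tumors of the oral cavity and oropharynx, as was the case in GT-001 and GT-201". Section 7.1 of the present protocol admits locally advanced squamous cell carcinoma of the head and neck without restriction by primary site, unknown primaries included. At least two oral sites must be planned to receive 50 Gy or more. Section 4.2 makes clear that the wider range of tumors is intended.

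**The concern.** A reader of the synopsis meets two statements that cannot both be right: an endpoint list confined to OM, and a key secondary endpoint on tumor outcome. If this stays, the study report must either leave out a declared endpoint or build one afterwards from whatever tumor data happen to be on file.

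The second issue concerns interpretation. If the all-subject SOM rate is set beside rates from trials restricted to two tumor sites, a difference may reflect the drug, scoring practice, region, open-label assessment or simply a different mix of sites. Agreement between the rates could hide offsetting effects. The mix of sites is the one element that the trial can easily display with its own data.

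**Working it through.** **Step 1. Look for the tumor endpoint.**

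- Objectives (Section 5.1): safety and SOM incidence only.
- Endpoints (synopsis and Section 5.2): adverse events, laboratory findings and OM only.
- Tumor status (Section 10.6): its only content is pre-treatment imaging, for consistency with eligibility.
- Schedule (Appendix 1, Table 5 and footnote 8): imaging at screening, within 60 days before radiotherapy starts. No later tumor assessment appears.
- Follow-up (Section 10.7.3.1): four weeks, listing OM, adverse events and concomitant medication.
- Efficacy analysis (Section 12.5): incidence and days of SOM and Grade 4 OM, descriptive.

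Two traces remain after baseline. Section 10.7.2.1 asks for a clinical tumor assessment on the last radiotherapy day or at early termination. It refers to Section 10.6.1, which holds no method for it, and Table 5 has no row for it. Section 11.2.4 has progression, if found, entered on case report form pages. Neither supplies a response criterion, a scan schedule or an analysis. For contrast, Section 4.2 reports tumor response through 1 year in GT-001 and tumor outcomes at two years in GT-201.

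**Step 2. Look for the comparison set.** Section 12.3 defines an all-treated set and a per-protocol set. Section 12.5 plans overall rates, and Section 12.5.3 marks covariate adjustment as not applicable. The protocol designates no subset, comparator arm or comparison statistic. The SOM rates in Section 4.2 (43% on 90 mg, 65% on placebo, GT-201) are background.

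**Step 3. What site mix could do.** Let f be the share of subjects with other primaries and d the gap between their SOM rate and that of the oral cavity/oropharynx subjects. The all-subject rate then differs from the subset rate by f × d. The documents give neither quantity. For illustration only, f of 20% to 40% and d of 10 to 20 points give 0.2 × 10 = 2 points up to 0.4 × 20 = 8 points, in either direction. These inputs are assumptions, so the result is not an estimate.

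**Step 4. What the subset costs in precision.** Exact (Clopper-Pearson) 95% limits for x events in n are the 2.5% quantile of Beta(x, n − x + 1) and the 97.5% quantile of Beta(x + 1, n − x). Inputs are the maximum of 70 subjects, a rate near 43%, and subsets of 70 × 0.8 = 56 and 70 × 0.6 = 42 (assumed).

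| Set | x/n | Exact 95% CI | Half-width |
|---|---|---|---|
| All subjects | 30/70 | 31.1% to 55.3% | 12.1 points |
| Subset, f = 20% | 24/56 | 29.7% to 56.8% | 13.5 points |
| Subset, f = 40% | 18/42 | 27.7% to 59.0% | 15.7 points |

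These widths are sampling error. They show the price of the subset, not the size of the site-mix effect.

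**Step 5. The plan's own figure.** The only design probability given is a 95% chance of seeing at least one case of a 1% adverse event among 300 subjects: 1 − 0.99^300 = 0.951. It reproduces, and this point does not affect it.

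**The case against.** **The sponsor could define the tumor endpoint instead of deleting it.** That is possible, but it would need criteria, time points, a method and an analysis that the design does not contain. A separate analysis plan cannot supply assessments that the protocol does not schedule. This part of the point stands.

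**The comparison may be settled elsewhere.** Section 12.1 gives a separate statistical analysis plan control over the analyses, and Section 12.6 sends exploratory analyses there. Its text is not part of the document reviewed. This objection stands, and the second half of the fix is conditional on it. A reader might infer that the plan has no comparison set at all; the documents show only that the protocol states none.

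**The sample size does not depend on the comparison.** Section 12.2 justifies up to 70 subjects by the 300-subject safety database alone. A reader might infer from the synopsis that the trial is too small for its efficacy purpose. The documents do not support that, because no precision or power target for SOM is stated.

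**The comparator is loosely named.** Only GTI-4419-301 is expressly placed in the US and Canada. The site restriction applies to all three earlier trials, though, so the mismatch remains whichever is meant. It is not shown for the historical controls: Section 4.1.1 gives about 70% SOM for head and neck cancer patients on radiotherapy plus single-agent cisplatin, with no restriction by site.

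**Eligibility already aligns exposure.** Requiring two oral sites at 50 Gy or more narrows the difference between populations by an unknown amount. This stands, and is one reason to give no estimate of bias.

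**The scoring claim is mostly wording.** Section 10.3 provides evaluator training, standardized assessment and vendor data quality management. A reader might infer that scoring uniformity is unprotected or rests only on the SOM rate; neither follows.

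**Conclusion.** The tumor-outcome inconsistency is settled by the text: one synopsis sentence claims an endpoint that the objectives, endpoint lists, schedule, follow-up and analysis do not carry. The consequence is for reporting. No hypothesis test, sample size or safety analysis depends on it.

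The comparison point holds in a limited form. An all-subject SOM rate set against the earlier GC4419 trials is confounded with tumor site, to a degree that cannot be estimated from the documents. It would be tempting to present the illustrative 2 to 8 points, or the 31% to 55% interval, as the size of the defect. The first rests on two assumed inputs, and the second would be present at 70 subjects whatever the mix of sites. Nor do the documents show that the subset alone is the right comparison. Showing both rates is a cheap improvement in transparency, but it leaves region and open-label assessment unadjusted.

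Both changes should be made, the second only if the separate analysis plan does not already cover it.

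**What to change.** 1. Remove tumor outcome as a key secondary efficacy endpoint from the synopsis statistical methods. Reconcile that paragraph with the synopsis endpoint list, Sections 5.2, 10.6, 10.7.2.1, 11.2.4 and 12.5, and Table 5. Whether the last-day tumor assessment stays is for the sponsor to decide.
2. Unless the separate statistical analysis plan already does so, record primary site explicitly and state in advance how unknown primaries are classed. The screening history in Section 10.7.1 does not list primary site by name.
3. When comparing with the 90 mg arms of the earlier trials, present the SOM rate with an exact 95% CI for the oral cavity plus oropharynx subset beside the all-subject rate. Label the comparison descriptive and unadjusted for region and open-label assessment.
4. Optional: reword the scoring-uniformity claim so that it does not rest on the SOM rate alone and refers to the training and vendor data quality management in Section 10.3.

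The cost is synopsis wording, some cross-references, one data item and one two-column table. Sample size, treatment and visits do not change. The downside is the wider subset interval shown in Step 4. Any comparison with GTI-4419-301 must also wait for its unblinded results, for which the documents give no date.
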